Cover Page

Study Title: *Chewed versus integral pill of ticagrelor in selected patients undergoing coronary angiography --a platelet reactivity study and patient outcomes study.*

NCT number: NCT03708588

Document/version date: 10/08/2020

Project title: Chewed versus integral pill of ticagrelor in in selected patients undergoing coronary angiography --a platelet reactivity study and patient outcomes study.

Principal Investigator: [name]

Address: [name]

[contact]

Email: [contact]

Lead Fellow: [name]

BACKGROUND

Patients with acute coronary syndrome (ACS) and stable coronary artery disease usually require percutaneous coronary intervention (PCI) with stent deployment to open stenosed or occluded coronary arteries. Ticagrelor (Brilinta) is an orally administered third generation thienopyridine and reversible P2Y12 receptor antagonist and has been shown to improve patient outcomes as compared to other antiplatelet medications. In the PLATO trial published in 2009, for example, patients with ACS treated with ticagrelor experienced a significantly lower rate of death, repeat myocardial infarction, and stroke.

Despite advancements in medical therapy, studies have demonstrated delayed antiplatelet effects of oral P2Y12 inhibitors and higher than expected platelet reactivity hours after drug administration. Due to elevated risk of peri-procedural thrombotic events in patients undergoing PCI, the goal of achieving platelet inhibition more rapidly should be addressed.

The delayed antiplatelet effects of medications like ticagrelor are likely related to impaired drug absorption. Many patients presenting with acute coronary syndromes have decreased gastrointestinal motility. Additionally, if morphine is administered by medical providers for chest pain absorption of antiplatelet medications such as ticagrelor may be delayed. Research performed to date has demonstrated more rapid absorption and platelet inhibition when ticagrelor is administered in crushed or chewed form to patients with ST segment elevation MI (STEMI)

In December 2017, a trial compared a chewed sublingual form of ticagrelor to standard pill form in patients with STEMI. It also showed more rapid absorption and platelet inhibition within hours of drug administration. To our knowledge, our study will be the first to compare platelet reactivity in non ST segment elevation acute coronary syndrome (NSTE-ACS) and patients with stable CAD undergoing PCI who received chewed ticagrelor.

Specific Aims:

To compare the effect of ticagrelor chewed pills with the effect of equal dose of integral pills in decreasing platelet reactivity and adverse event rates in all patients being treated for NSTE-ACS and stable coronary artery disease, undergoing percutaneous coronary intervention.

Primary objective:

Determine platelet inhibition at baseline, and early at 1 hour and 4 hours after loading dose.

Secondary objective:

Assess major adverse cardiac and cerebrovascular event (MACCE) rate at 30 days and 1 year.

1. Death;
2. Repeat myocardial infarction;
3. Need for urgent revascularization;
4. Cerebrovascular accident;
5. Rate of stent thrombosis and in-stent stenosis at 30 days and 1 year;
6. Bleeding: Defined as major, minor, or minimal bleeding based on TIMI criteria.

Hypothesis:

Chewed ticagrelor pill is superior to integral pill in decreasing platelet reactivity.

Primary Outcome Measures:

Residual platelet reactivity by Platelet Reactivity Units (PRU) VerifyNow 1 hour and 4 hours after ticagrelor loading dose (LD) and percent of patients with a high residual platelet reactivity (PRU > 208) 1 hour and 4 hours after ticagrelor LD.

Secondary Outcome Measures:

1. Bleeding events: Major, minor, minimal bleeding (TIMI criteria) events.
2. Occurrence of dyspnea and/or symptomatic bradycardia.
3. Major adverse cardiac and cerebrovascular event (MACCE) rate: Death, Myocardial infarction, Stent Thrombosis, Urgent revascularization, Cerebrovascular accident at 30 days and 1 year.

STUDY DESIGN

This will be an interventional study to evaluate the superiority of chewed ticagrelor in comparison to integral pill form. Superiority will be defined as a reduction of platelet reactivity in both groups undergoing PCI.

Study population will include 132 patients. They will be stratified into 2 groups: Patients with NSTEMI-ACS and patients with stable coronary artery disease (CAD) undergoing coronary angiography for non-urgent reasons.

Inclusion criteria:

- 4. Patients presenting with NSTEMI-ACS or stable CAD undergoing coronary angiography for urgent or non-urgent reasons.

Exclusion criteria:

1. Age <18 years or Age >90 years;
2. Known coagulopathy, bleeding diathesis, or active bleeding;
3. Known chronic therapy with clopidogrel, prasugrel, or ticagrelor;
4. Known history of intracranial bleed or intracranial neoplasm;
5. Suspected aortic dissection;
6. Severe hemodynamic instability, cardiogenic shock;
7. Life expectancy <1 year;
8. Known severe liver or renal disease (CrCl < 30, or dialysis dependent);
9. Taking drugs known to interfere with CYP3A4 metabolism (Azoles, Clarithromycin, Ritonavir, Saquinavir, Nelfinavir, Indinavir, Atazanavir);
10. Any use of GP IIb-IIIa inhibitors 48-hours before the procedure or any use during the procedure;
11. Any use of Cangrelor during or after the procedure;
12. Hemoglobin <10 g/dL, PLT <80x10⁹/L;
13. Pregnant or lactating females;

14. Known allergy to study medication;
15. Fibrinolytic use within past 48 hours;
16. Inability to give consent;
17. Known sick sinus syndrome (SSS) or high degree AV block without pacemaker protection.

Written informed consent:

Patients presenting for both urgent and elective left heart catheterization will be consented by the personnel delegated by the investigator before any study-related activity.

Randomization:

Patients will be randomized prior to PCI. Patients from each strata (NSTE—ACS, and patients with stable CAD) will be randomized in a 1:1 fashion to receive a loading dose of 180mg ticagrelor in integral pill form (swallowed) or chewed form.

Study procedures:

Patients admitted to the inpatient cardiology service with NSTE-ACS meeting eligibility criteria are often treated medically before reaching the catheterization suite for coronary angiography and possible percutaneous coronary intervention. These patients often receive the loading dose of 180mg ticagrelor on the medical floor. In order to enroll these patients, the baseline PRU level blood draw, can be obtained on the floor before that loading dose is administered. The subsequent 1-hour and 4-hour blood draws can be obtained on the medical floor or in catheterization suite.

[figure not shown]
Patients scheduled to undergo and elective (non-urgent) coronary angiography for stable CAD who meet eligibility criteria will have blood drawn for a baseline PRU level prior to administration of the study drug. After the procedure, two subsequent blood draws will be taken at precise times: 1 hour +/-60 minutes, and 4 hours +/- 90 minutes after loading dose administration. All other procedures are considered standard of care.

Arm	Intervention/Treatment
Arm One: Chewed ticagrelor pills (Loading dose 180mg)	Drug: Ticagrelor chewed pills. The loading dose will be administered as soon as possible by hospital floor nurse or Catheterization Lab staff after a baseline PRU level is drawn. Patients will be asked to

	chew and swallow followed by 25-50mL of water.
Arm Two: Integral pill form of ticagrelor (Loading dose 180mg)	Drug: Ticagrelor integral pills. The loading dose will be administered as soon as possible by hospital floor nurse or Catheterization Lab staff after a baseline PRU level is drawn. and before the end of the PCI . Patients will swallow the loading dose followed by 25-50mL of water.

Subject will have orders to continuing ticagrelor during admission status. After the 4th hour blood draw the primary outcome will be complete. Patients will be encouraged to remain on ticagrelor with an outpatient prescription to measure secondary outcomes.

Flow Chart

Patient's EMR will be reviewed at 30 days and at 1 year to document any primary or secondary outcome measures. Duration of the study is one year.

Data collection

Baseline Characteristics	Procedure Related information	Post-procedure Related Information
Gender		
Body mass index, kg/m ²	Consenting	PRU 1 hour
Current smoker	Randomization	PRU 4 hours
Hypertension	Baseline PRU test	Length of stay
Diabetes mellitus	Loading dose administration	Date of death
Dyslipidemia	Access (femoral, Radial)	Repeat MI
Prior coronary artery disease	Start catheterization	Stent thrombosis 30 days
Prior aspirin	Culprit vessel	CVA
Prior beta-blockers	Type of stent	Urgent Revascularization
Prior statins	Number of stents	
LVEF (%)	Fluoro time/dose	
Creatinine clearance, mL/min	Contrast volume	TIMI Minimal bleeding
Hemoglobin (gr/dl)	Narcotic use	TIMI Minor bleeding
Platelet count, 1,000/mm ³		TIMI Major bleeding
Low-density lipoprotein (mg/dl)		Access site complication (hematoma, pseudoaneurysm, need for surgical or percutaneous repair)
High-density lipoprotein (mg/dl)		

Data will be collected by the personnel delegated by the PI. Preliminary data will be analyzed after enrollment of 65 patients.

Timeline /Schedule of events

	Visit 1 Baseline	Visit 2 Procedure	Visit 3 Post Procedure	Visit 4 Discharge	Visit 5 30 day follow up- (+/- 14 d) EMR-Chart review	Visit 6 1 yr follow up- (+/- 14 d) EMR-Chart review
Inclusion/ Exclusion	X					
Informed Consent Obtained	X					
Demographics, Medical History, Con Meds	X					
Angiography /PCI Procedure		X				
Blood draw for PRU	X baseline, 1-hour and 4- hour levels can be collected before coronary angiograp hy for patients admitted to hospital floor	X	1 h after PCI 4h after PCI			

	before procedure					
MAACE Event documentation				X	X	X

Statistical Analysis

Patient characteristics will be presented as proportions for categorical variables and mean \pm standard deviation (SD) and or Median [lower quartile (01) - upper quartile (03)] for continuous variables. Comparison of categorical variables for patients who will receive integral pill form of ticagrelor and the other the chewed form will be performed using the chi-square and Fisher's exact test while the two sample t test will be done to assess differences in continuous patient characteristics. Visual displays of event free Survival and cumulative incidence curves will be generated by the Kaplan-Meier approach and event free survival among groups compared using the log rank test. In addition to time point analysis, an alternating logistic regression (ALR) will be fitted to evaluate P2Y12 reaction units (PRU) levels at baseline (before LD), 1 hour, and 4 hours. Further analysis will entail fitting both univariate and multivariate Cox proportional-hazards models to examine the association between baseline characteristics and each of outcomes: In-stent thrombosis and restenosis, MACCE, and the need for repeat revascularization within 1-year separately. All analyses will be done using SAS Version 9.4 (SAS Institute, Cary, NC) and tests performed at a 5% level of significance.

Monitoring Plan

The goal of monitoring in this study is primarily to make sure that the primary data are collected and recorded properly and consenting process was done.

The Principal Investigator will be responsible for monitoring the safety environment of the participants, and will ensure that

- a) Only subjects who meet the study eligibility criteria will be enrolled. All subject inclusion/exclusion criteria were reviewed and verified with source documents, when applicable.
- b) The informed consent process will be obtained prior to proceeding with any study procedures. Any problems with informed consent will also be documented, and reported to the IRB, if required.
- c) Data is collected and analyzed as specified in the protocol.
- d) Adverse events are reviewed promptly and reported as required.
- e) Privacy and confidentiality of subjects is maintained. Consent forms will be stored in a room accessible only to research personnel.
- f) Subject withdrawals will be documented for the reason of withdrawal.
- g) Subjects will be informed during the informed consent process that study results may be disseminated in the form of presentations at conferences and publications in journals. The data/results that will be presented will only include anonymous/aggregate data, nothing that will identify subjects.
- h) A regulatory binder will be kept to document: IRB approvals, protocol versions, informed consents (all versions), all formal communications with the IRB (approval letters,

acknowledgements), Delegation of Authority Log.

This study will be listed on ClinicalTrials.gov prior to enrollment of subjects.

<https://clinicaltrials.gov/ct2/manage-recs/fdaaa>

Human Protections

This prospective randomized trial may require patients to undergo additional lab draws at intervals described above if samples cannot be taken from peripheral intravenous (IV) lines already in place. Risks associated with lab draws include, but are not limited to, bleeding, infection, and patient discomfort. Highly trained technicians will be drawing blood, if required, to mitigate the risks described above. Breaching patient confidentiality will be minimized by storing subject information in password-protected devices and by limiting access to data to those named on the IRB form. Additionally, data will be reported in aggregate form only.

Dissemination and Future Funding Plan

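### One superiority claim rests on four unranked primary PRU readings, and the plan does not say which result decides it

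*Combined protocol and SAP*

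**What the plan says.** The Hypothesis is one statement: "Chewed ticagrelor pill is superior to integral pill in decreasing platelet reactivity". It names no time point and no scale.

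The Primary Outcome Measures give residual PRU by VerifyNow at 1 h and 4 h after the loading dose, joined by the word *and* to "percent of patients with a high residual platelet reactivity (PRU > 208) 1 hour and 4 hours after ticagrelor LD". The Primary objective likewise sets the two times side by side: "Determine platelet inhibition at baseline, and early at 1 hour and 4 hours after loading dose".

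Study Design contains the only success definition: "Superiority will be defined as a reduction of platelet reactivity in both groups undergoing PCI". It comes after a sentence comparing the two pill forms and shortly before the one that splits patients into NSTE-ACS and stable CAD strata.

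Statistical Analysis plans two routes for PRU without saying which decides: "In addition to time point analysis, an alternating logistic regression (ALR) will be fitted to evaluate P2Y12 reaction units (PRU) levels". It closes with "tests performed at a 5% level of significance". The section mentions no hierarchy, adjustment or rule for discordant results. The Background gives the motivation: "the goal of achieving platelet inhibition more rapidly should be addressed".

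**The concern.** A single claim needs a single rule that turns results into a yes or a no. Here four results feed the claim and the rule is missing. Suppose chewed wins on continuous PRU at 1 h but not at 4 h, or on PRU > 208 alone. Nothing in the plan says whether superiority has been shown, so the choice can be made after the results are known.

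Two things are at stake. The first is error: if the choice falls on whichever reading is significant, the stated 5% no longer describes the risk of a false claim. The second is meaning: the claim could rest on a reading that was not chosen in advance as the test of faster inhibition.

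**Working it through.** **Inputs from the protocol.** Four primary readings (2 scales × 2 times). Each test is at 5%; sidedness is not stated and two-sided is assumed, so 2.5% favours chewed. There are 132 patients randomised 1:1, hence 132 / 2 = 66 per arm. No PRU mean, SD, high-reactivity rate, effect size or power is given, so the figure of 132 cannot be reproduced and every PRU input below is an assumption.

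**Step 1: independent tests, as an upper-end figure.**
- Either direction: 1 − 0.95⁴ = 18.5%.
- Favouring chewed only: 1 − 0.975⁴ = 9.6%.
- Counting the alternating logistic regression as a fifth test: 1 − 0.95⁵ = 22.6%.

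Independence cannot hold, because PRU > 208 is a cut of the same PRU value.

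**Step 2: correlated readings, simulated with no true difference.** Each scenario has 20,000 trials, 66 per arm, normally distributed PRU, t tests on PRU and two-proportion z tests on PRU > 208. PRU at 1 h is assumed to be 150 ± 90. The table shows the chance of at least one significant reading in either direction.

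| Assumed 4-h PRU | Correlation 0.3 | 0.5 | 0.7 |
|---|---|---|---|
| 60 ± 55 (almost nobody above 208) | 12.2% | 11.8% | 11.1% |
| 120 ± 80 (some above 208) | 15.8% | 15.2% | 14.2% |

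A second simulation (40,000 trials per scenario) assumed 30–60% above 208 at 1 h, 5–20% at 4 h, and correlations from 0 to 0.9. It gave 12.6–16.3%.

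**Step 3: only results favouring chewed.** This is the error that matters for the claim. The first set of assumptions gives about 5.5–7.6% and the second 6.3–8.3%, against 2.5%. Statistical Analysis names both chi-square and Fisher's exact test for categorical comparisons. With Fisher throughout, the first set gives 4.9–6.2% favouring chewed and 10–12% in either direction.

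**Step 4: other readings of the missing rule.**
- If significance were required in each of two strata on the same reading, the chance per reading is 0.05² = 0.0025, and over four independent readings 1 − (1 − 0.0025)⁴ = 1.0%. With equal strata (an assumption) there are 33 per arm in each. Power for an assumed 0.5 SD difference is then 53% per stratum, and 0.53² ≈ 28% for both.
- If all four readings had to be significant, the false-claim rate is well under 1%. The trial could then hardly succeed if PRU > 208 at 4 h is rare in both arms.

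The false-claim rate therefore runs from under 1% to about 16% according to a rule that the plan does not state.

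**Step 5: after the change.** With one named primary the error is 5% (2.5% favouring chewed), and power at 66 per arm is 82% for an assumed 0.5 SD difference. If all four readings are kept with a Bonferroni split, each is tested at 0.05 / 4 = 0.0125. Power per reading then falls to 65%, and about 180 patients would be needed for 80% power, against 126 at 5% (normal approximation, no dropout).

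**The case against.** The strongest reply is that the plan nowhere says one win is enough. A reader might infer that superiority may be claimed on any one of the four readings, but the documents do not support that as a stated rule. The readings are joined by *and*, which could mean all four. The success definition, if its two groups are the strata, could demand more than one significant result. This stands: the defect is silence, not a permissive rule. It does not close the gap, because the definition still names no reading and does not ask for significance per stratum.

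A reader might also infer that the 4-h draw is a late measure that does not match the question, or that it mainly shows the arms converging. The documents do not support this either. The Primary objective calls both times early, the Background speaks of raised reactivity hours after dosing, and nothing in the text shows convergence by 4 h. The 1-h draw is the closer fit to more rapid inhibition, but the 4-h draw is a legitimate outcome.

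It may be said that the alternating logistic regression supplies one joint test. It is a method for repeated binary outcomes, so it does not settle continuous PRU, and it is planned in addition to the time-point tests.

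Finally, naming the 1-h draw puts weight on a loosely timed sample. This stands too, and the timing has to be dealt with in the same change.

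**Conclusion.** The concern holds as a missing decision rule: four primary readings, one superiority claim, 5% for each test, and no statement of which result decides. If any one significant reading were accepted, the false-result rate would be about 11–16% in either direction, or about 5.5–8% favouring chewed; the 18.5% figure is only the upper end under independence. The sizes rest on assumed PRU distributions, 66 per arm, two-sided tests and no missing samples. Exact tests lower them somewhat, but the rate favouring chewed stays at about twice the nominal 2.5%. That the rule is missing depends on none of these assumptions. The change should be made, since it settles what the trial may claim.

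**What to change.** Before outcome data by arm are seen, amend the outcome and statistics sections as follows.

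1. Name continuous PRU at the 1-h draw as the single primary outcome, tested at 5%, and state that superiority rests on it.
2. Test the others in fixed order, each only if the one before is significant: continuous PRU at 4 h, PRU > 208 at 1 h, PRU > 208 at 4 h. Putting 4-h PRU second keeps a less sensitive binary cut from blocking a continuous reading.
3. Define the two groups in the success definition (strata or otherwise) and say whether significance is required in each.
4. Reconcile the timing of the 1-h draw. Study procedures count it from the loading dose with a window of ±60 minutes, that is 0 to 2 h; the schedule of events lists it as 1 h after PCI.
5. State the role of the alternating logistic regression, for example as supportive.

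No new patients or data are needed. The downside is that a difference seen only at 4 h or only in PRU > 208 could not be claimed as the primary result. If the sponsor wants both times and both scales to carry the claim, a stated alpha split would also close the gap, at the loss of power shown above. The protocol plans a preliminary analysis after 65 patients and does not say how far enrolment has gone, so the amendment should be dated and should record whether any results by arm had been seen.

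### The success rule does not say whether chewed must win in each stratum or overall, and its PCI wording does not match a population enrolled for angiography

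*Combined protocol and SAP*

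**What the plan says.** **The rule.** The Hypothesis is one overall statement: "Chewed ticagrelor pill is superior to integral pill in decreasing platelet reactivity". Study Design says the trial will "evaluate the superiority of chewed ticagrelor in comparison to integral pill form" and then defines success: "Superiority will be defined as a reduction of platelet reactivity in both groups undergoing PCI". The next paragraph adds "Study population will include 132 patients" and "They will be stratified into 2 groups", these being NSTE-ACS and stable CAD. Under Randomization, allocation is 1:1 within each stratum.

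**The population.** The Specific Aims place the comparison "in all patients being treated for NSTE-ACS and stable coronary artery disease, undergoing percutaneous coronary intervention". The title instead says "in selected patients undergoing coronary angiography", and the one visible inclusion criterion reads "Patients presenting with NSTEMI-ACS or stable CAD undergoing coronary angiography for urgent or non-urgent reasons". The stable-CAD stratum is described by non-urgent angiography, and the consent text by urgent or elective left heart catheterization.

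**The timing.** Randomisation comes before PCI. Under Study procedures, NSTE-ACS inpatients often receive the loading dose on the ward, when PCI is described only as a possibility. Their 1-hour and 4-hour samples may be drawn there, and the schedule of events allows this before angiography. The primary outcome is said to be complete at the 4-hour draw.

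**The analysis.** Statistical Analysis assigns the two-sample t test to continuous characteristics of the patients. It mentions analysis by time point without naming a test, and fits an alternating logistic regression to PRU at three times in a sentence that names neither arm nor stratum. The level is 5%, with sidedness not given. Data collection plans an analysis of preliminary data after 65 patients.

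**The concern.** The chewed-versus-integral contrast is clear from the Hypothesis. The rule does not turn it into a test, in two respects.

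First, the paragraph after the rule uses the word groups for the strata, so the rule most naturally refers to NSTE-ACS and stable CAD. It may then require chewed to win in each stratum, or only in the two taken together. The same data can succeed under one reading and fail under the other.

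Second, the rule is worded for PCI patients, while enrolment is worded for angiography. For ward-dosed patients, PCI status is settled after randomisation and possibly after both PRU samples. Nothing says how a randomised patient without PCI is handled. Read literally, the rule sets aside patients who have already supplied the primary outcome.

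If the 65-patient analysis includes PRU by arm, either choice could be made after those results are known.

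**Working it through.** **Inputs.** From the documents: 132 patients (Study Design), 1:1 allocation within strata (Randomization), hence 66 per arm, and a 5% level (Statistical Analysis). Assumed because the documents do not give them: two-sided testing, the pooled power, the same true effect in both strata, the stratum split and the share having PCI.

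**Step 1: the plan's own figure.** 132 cannot be reproduced, because no effect, SD, event rate or power is stated. As a reference point, suppose it gives 80% pooled power. The expected z is then 1.960 + 0.842 = 2.802, which corresponds to a standardised difference of 2.802 × √(2/66) = 0.488.

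**Step 2: pooled or each stratum.** A stratum holding a share s of the patients has expected z = 2.802 × √s and power Φ(2.802√s − 1.96). The strata are independent, so the power to win in both is the product.

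| Stratum split | Power in each | Power to win in both |
|---|---|---|
| 50/50 | Φ(1.981 − 1.96) = 0.508, both strata | 0.508² = 0.258 |
| 70/30 | 0.650 and 0.335 | 0.218 |

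Starting from 90% pooled power (expected z 3.242), the equal-strata result is 0.630² = 0.397. Calculations based on the t distribution give 0.252 and 0.212 in place of the two table results, so the approximation is adequate here.

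If both equal strata reach z = 1.96, the pooled z is at least (1.96 + 1.96)/√2 = 2.77, so a win in both implies a pooled win. At 80% pooled power the two readings therefore disagree in 0.800 − 0.258 = 0.542 of trials, always with the pooled reading succeeding and the each-stratum reading failing.

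**Step 3: the PCI condition.** If 132 counts all randomised patients and a share f has PCI, the power in PCI patients is Φ(2.802√f − 1.96).

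- f = 0.7: Φ(2.344 − 1.96) = 0.650
- f = 0.9: Φ(2.658 − 1.96) = 0.757

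If 132 counts PCI patients only, no power is lost. Then 132/0.7 ≈ 189 or 132/0.9 ≈ 147 must be randomised, and 57 or 15 of them fall outside the rule.

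**Step 4: where PCI status follows randomisation.** For ward dosing the permitted order is randomisation, dose, 1-hour and 4-hour samples, then angiography and perhaps PCI. For laboratory dosing the text requires only that randomisation precede PCI, so it may follow the diagnostic angiogram, with PCI already decided.

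**The case against.** The strongest reply is that this is loose wording. The Hypothesis is a single statement and the Aims speak of all patients, both of which favour pooling. The schedule has one combined row for angiography and PCI, which suggests that the terms are used interchangeably. No passage expressly excludes patients without PCI, and the Background says these patients usually need it. All this is fair and makes a pooled, all-randomised intention plausible. It does not establish one: the success rule itself points to the strata and to PCI, and the analysis section settles neither.

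Two limits on the PCI part stand. Patients dosed in the catheterization laboratory may have been randomised after PCI was decided, so the problem may not apply to them. The visible inclusion list also begins at item 4, and figure content is missing. Items lost in extraction could narrow the mismatch, for example if one required planned PCI.

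A reader might infer more than the documents support:

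- **Bias.** Nothing suggests that pill form changes who goes on to PCI.
- **Inflated type I error from an each-stratum rule.** That rule is conservative: with no effect in either stratum, the chance of a favourable win in both is 0.025² = 0.0006.
- **No comparator.** Taken alone, the rule could mean a fall from baseline in both arms, but the Hypothesis and the preceding sentence give the contrast.
- **A planned unblinded look.** The 65-patient analysis is not said to use PRU or arm.

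**Conclusion.** The point holds and should be fixed. The only success rule leaves open whether chewed must win in each stratum or overall. Its PCI wording conflicts with enrolment for angiography and, for ward-dosed patients, makes membership of the analysis depend on an event after randomisation.

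The size is illustrative. With the same effect in both strata and equal stratum sizes, 80% pooled power corresponds to about 26% for a win in both (22% at a 70/30 split). If 132 counts all randomised patients and 70% to 90% have PCI, 80% becomes about 65% to 76%; at the upper end the loss is small. A reader might conclude that the trial is underpowered. The documents do not support that, because they state no target power, effect or SD. What is shown is that the choice of reading can change the verdict.

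**What to change.** Replace the rule in Study Design with:

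> Superiority is concluded if platelet reactivity [deciding measure and time point named by the sponsor] is lower in the chewed than in the integral arm among all randomised patients with a PRU measurement, whether or not PCI follows, at the two-sided 5% level.

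Add to Statistical Analysis:

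> The primary comparison is by randomised arm, using a linear model with arm, stratum (NSTE-ACS/stable CAD) and baseline PRU, or a Cochran-Mantel-Haenszel test stratified by NSTE-ACS/stable CAD if PRU > 208 decides. Stratum-specific and PCI-only estimates with 95% confidence intervals are supportive.

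In the Specific Aims, align only the platelet-reactivity part with the angiography population, and keep PCI or stented patients as the denominator for stent-related outcomes. State how patients who meet exclusion criteria 10 or 11 during or after the procedure enter the analysis, since those criteria can be met after randomisation. Make the edits before any PRU comparison by arm, including any at 65 patients.

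If a win in each stratum is intended, say so and give the resulting power. If PCI patients are the intended population, say so and state whether 132 counts them.

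The cost is text in three sections, with no new visits or samples. The data collection table lists stent fields but no explicit PCI item, so one yes/no field may be needed for the PCI-only estimates. The price is that there is no separate confirmatory claim per stratum or for PCI patients, a pooled estimate averages over any difference between strata, and the sponsor must commit to one deciding measure and time point.
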